8.6 Data and Safety Monitoring Plan

The Principal Investigators will provide continuous monitoring of subject safety in this trial with periodic reporting to the Data and Safety Monitoring Committee (DSMC). The Principal Investigators responsible for the care of all subjects in this study will also oversee the conduct of safety data review meetings on a regular basis. Bi-weekly safety review meetings will be instituted upon study enrollment as soon as a subject(s) enters the study, has received treatment with durvalumab and radiation therapy during Cycles 1-3, and the during the post-treatment evaluation period. These meetings will include the investigators as well as study coordinators, data coordinators, regulatory associates, clinical data management associates, and any other relevant personnel the principal investigators may deem appropriate. At these meetings, the research team will discuss all issues relevant to study progress, including enrollment, safety, regulatory issues, data collection, etc. An agenda and minutes will be generated for each meeting to document attendees and subject data reviewed.

Meeting summaries will be available for inspection when requested by any of the regulatory bodies charged with the safety of human subjects and the integrity of data including, but not limited to, the oversight (Office of Human Research Ethics (OHRE) Biomedical IRB, the Oncology Protocol Review Committee (PRC) or the North Carolina TraCS Institute Data and Safety Monitoring Board (DSMB).

The UNC LCCC Data and Safety Monitoring Committee (DSMC) will review the study on a regular (quarterly to annually) basis, with the frequency of review based on risk and complexity as determined by the UNC Protocol Review Committee. The UNC PI will be responsible for submitting the following information for review: 1) safety and accrual data including the number of patients treated; 2) significant developments reported in the literature that may affect the safety of participants or the ethics of the study; 3) preliminary response data; and 4) summaries of team meetings that have occurred since the last report. Findings of the DSMC review will be disseminated by memo to the UNC PI, PRC, and the UNC IRB and DSMB.

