PROTOCOL AMENDMENT #4

LCCC 1725: A Phase II Study of Durvalumab (MEDI 4736) with Radiotherapy for the adjuvant treatment of Intermediate Risk Head and Neck Squamous Cell Carcinoma

AMENDMENT INCORPORATES (check all that apply):

Editorial, administrative changes
 Scientific changes (IRB approval)
 Therapy changes (IRB approval)
 Eligibility Changes (IRB approval)

The purpose of this amendment is to change accrual for the study to 18 subjects. Statistical considerations in light of this change have been updated to accommodate the new accrual. [name] designation was updated.

Editorial Changes

1. Where appropriate in the header, [name] designation was changed from MD to DO.

Scientific Changes

1. Section 1.1 and Schema have been updated to accommodate new accrual numbers.
2. Section 5.1: Updated Schema to accommodate new accrual numbers.
3. Section 9.2 has been updated to include new statistical descriptions relative to the change in accrual.

THE ATTACHED VERSION DATED June 1, 2021 INCORPORATES THE ABOVE REVISIONS

ATTACH TO THE FRONT OF EVERY COPY OF PROTOCOL

PROTOCOL AMENDMENT #3

LCCC 1725: A Phase II Study of Durvalumab (MEDI 4736) with Radiotherapy for the adjuvant treatment of Intermediate Risk Head and Neck Squamous Cell Carcinoma

AMENDMENT INCORPORATES (check all that apply):

Editorial, administrative changes
 Scientific changes (IRB approval)
 Therapy changes (IRB approval)
 Eligibility Changes (IRB approval)

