1.5.2 Radiation Therapy + Durvalumab

In a single center subset of patients with solid malignancies, a phase I/II trial of durvalumab in combination with radiotherapy in the palliative setting was shown to be safe. The median duration of exposure to durvalumab was 5.2 months with a median delivery of 11 cycles (range, 4-38 cycles). RT (conformal 3D RT, 79% and intracranial stereotactic RT, 21%) was delivered at 28 Gy (range, 6-92), in a median number of five fractions (range, 1-10) and over a median duration of 6 days (range, 1-14). Five patients (50%) reported an irradiation-related adverse event grade 1 or 2 and one patient had two grade 2 AEs. The most frequently reported AE was grade 2 mucositis. There were no grade three or higher AEs.

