8.2 Durvalumab AEs of Special Interest

An adverse event of special interest (AESI) is one of scientific and medical interest specific to understanding of the Investigational Product and may require close monitoring and rapid communication by the investigator to the sponsor. An AESI may be serious or non-serious. The rapid reporting of AESIs allows ongoing surveillance of these events in order to characterize and understand them in association with the use of this investigational product.

AESIs for durvalumab include but are not limited to events with a potential inflammatory or immune-mediated mechanism and which may require more frequent monitoring and/or interventions such as steroids, immune-suppressants and/or hormone replacement therapy. These AESIs are being closely monitored in clinical studies with durvalumab monotherapy. An immune-mediated adverse event (imAE) is defined as an AESI that is associated with drug exposure and is consistent with an immune-mediated mechanism of action and where there is no clear alternate etiology. Serologic, immunologic, and histologic (biopsy) data, as appropriate, should be used to support an imAE diagnosis. Appropriate efforts should be made to rule out neoplastic, infectious, metabolic, toxin, or other etiologic causes of the imAE.

If the Investigator has any questions in regard to an event being an imAE, the Investigator should promptly contact the Study Physician.

AESIs observed with durvalumab include:

- Diarrhea / Colitis
- Intestinal perforation
- Pneumonitis / ILD
- Hepatitis / transaminase increases Neuropathy / neuromuscular toxicity (e.g. Guillain-Barré, and myasthenia gravis)
- Endocrinopathies (i.e. events of hypophysitis, hypopituitarism adrenal insufficiency, diabetes insipidus, hyper- and hypothyroidism, thyroiditis, and type I diabetes mellitus)
- Rash / Dermatitis
- Nephritis / Blood creatinine increases
- Pancreatitis/serum lipase and amylase increases
- Myocarditis
- Myositis / Polymyositis
- Other inflammatory responses that are rare / less frequent with a potential immune-mediated aetiology include, but are not limited to, pericarditis, sarcoidosis, uveitis and other events involving the eyeskin, haematological and rheumatological events, vasculitis, non-infectious meningitis and non-infectious encephalitis

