8.4.2 Documentation and Notification

SAEs or Serious SARs must be recorded in the SAE console within OncoreTM for that patient within 24 hours of learning of its occurrence. Additionally, the Multicenter Project Manager must also be notified via email of all SAEs within 24 hours of learning of its occurrence.

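### Section 8.6 requires layered safety review, but no trial-level toxicity count pauses accrual or calls an unscheduled DSMC review, and the safety criterion in 9.3 is undefined

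*Combined protocol and SAP*

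**What the plan says.** The plan requires oversight at several levels.

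- Section 8.6: the Principal Investigators monitor safety continuously. "Bi-weekly safety review meetings will be instituted upon study enrollment as soon as a subject(s) enters the study", with agenda and minutes. The LCCC DSMC "will review the study on a regular (quarterly to annually) basis, with the frequency of review based on risk and complexity"; the Protocol Review Committee sets that frequency.
- Section 8.4.2: the Multicenter Project Manager "must also be notified via email of all SAEs within 24 hours of learning of its occurrence".
- Section 8.2: events of special interest, serious or not, "may require close monitoring and rapid communication by the investigator to the sponsor".
- Section 8.5.3: an increased rate of serious suspected adverse reactions goes into an IND safety report.
- Sections 5.8 and 12.1: holds and discontinuations for the individual patient.

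On acute toxicity, endpoint 3.2.1 counts Grade 3-5 events from the first immunotherapy dose to 30 days after concurrent treatment, including those due to radiation. Section 9.3 tabulates this rate to decide whether a safety criterion is met and points back to earlier text for it. No such criterion appears there. A methods paper on continuous toxicity monitoring is reference 29, but the public text never cites it.

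Section 1.2.1 gives reference Grade 3-5 acute toxicity rates of 34.4% for postoperative radiotherapy alone and 77% with cisplatin.

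**The concern.** The people who would see excess toxicity are in place, but nothing agreed in advance tells them when to pause. The reporting duties carry timelines without a count, and the stopping rules apply to one patient at a time. Grade 3 events that are neither serious nor of special interest, mainly radiation effects, count toward endpoint 3.2.1. They are assessed on Day 1 of each cycle (Section 7.1) and can be raised bi-weekly. Their only documentation minimum is monthly (Section 8.3), however, and no running tally is required.

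These patients have had curative-intent surgery, and radiotherapy alone is one of their usual options (Sections 1.1 and 1.2). The durvalumab-radiotherapy series in Section 1.5.2 reports "There were no grade three or higher AEs", but it was palliative, with 28 Gy in a median of five fractions, against 60 Gy in 30 fractions here. Without a number, the decision to pause depends on who is in the room.

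**Working it through.** **What there is to reproduce.** The plan prints no toxicity boundary. Its one design calculation concerns 3-year DFS: [(1.2816·√(0.608·0.392) + 0.8416·√(0.838·0.162)) / 0.23]² = 16.55, so 17 evaluable, as Section 9.2 states for a one-sided alpha of 0.10. Toxicity plays no part in it.

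**Prior series.** Section 1.5.2 says "Five patients (50%) reported an irradiation-related adverse event grade 1 or 2", which implies 10 patients (inferred, not stated). Zero of 10 has an exact two-sided 95% upper limit of 1 − 0.025^(1/10) = 30.8%. That lies below the plan's own 34.4% for radiotherapy alone, so the series does not represent the 60 Gy setting.

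**Example boundary.** Inputs: N = 18 (Section 9.2). Assumed: acceptable rate p0 = 50%, overall false trigger at most 10%. After n evaluated patients, pause at the smallest k with P(X ≥ k | n, p0) ≤ g, where g is tuned so that total crossing at p0 stays within 10%. This gives 5 of 5, 6 of 6, 7 of 7-8, 8 of 9, 9 of 10-11, 10 of 12-13, 11 of 14, 12 of 15-16 and 13 of 17-18.

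Because of these steps, a first crossing can occur only at n = 5, 8, 11, 13, 16 or 18. Exact binomial paths give, at a true 77%, 0.271, 0.185, 0.126, 0.116, 0.069 and 0.063, which sum to 0.83.

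**Outcome lag.** Cycles 1-3 last 63 days, and the window adds 30, so an outcome is complete at day 93. Section 9.2 gives no accrual rate, so I assume 24, 12 or 6 months. Spacing is then about 41, 20 or 10 days, and 2, 4 or 9 further patients enter before an outcome is known. Patients treated = min(18, n + lag).

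- Accrual remains only if n + lag < 18. With a lag of 2 or 4 this admits n = 5, 8, 11 and 13, so at 77%: 0.271 + 0.185 + 0.126 + 0.116 ≈ 0.70. With a lag of 9 it admits n = 5 and 8: 0.271 + 0.185 ≈ 0.46.
- Patients spared at 77%, 24 months: 11(0.271) + 8(0.185) + 5(0.126) + 3(0.116) ≈ 5.4.

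| True Grade 3-5 rate | Crosses at any time | Crosses with accrual left: 24 or 12 months / 6 months | Spared of 18: 24 / 12 / 6 months |
|---|---|---|---|
| 34.4% | 1% | under 1% | 0.1 or less |
| 50% | 10% | 8% / 5% | 0.6 / 0.5 / 0.1 |
| 60% | 30% | 22% / 13% | 1.7 / 1.2 / 0.4 |
| 77% | 83% | 70% / 46% | 5.4 / 4.0 / 1.3 |

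Toxicities averted (rate × spared) are 4.2, 3.1 or 1.0 at 77%, at most 1.0 at 60% and at most 0.3 at 50%.

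**Late start.** These figures apply the rule from patient 1. The Amendment 4 cover sheet says "The purpose of this amendment is to change accrual for the study to 18 subjects" but not how many were already treated. If the rule starts after 12 are enrolled, patients spared at 77% fall to 3.3, 3.1 or 1.3; after 15, to 1.9, 1.7 or 0.9.

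**Other choices.** A 34.4% boundary with 5% false trigger is crossed in 32% of trials at a true 50% and 64% at 60%. A 60% boundary with 10% is crossed in 10% at 60% but only 52% at 77%.

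**The case against.** The strongest reply is that the trial is already watched closely. The spared figures compare the boundary with a trial that never pauses, even at 77%, and Section 8.6 makes that comparator unrealistic. At 24-month accrual, one patient enters about every 41 days. The bi-weekly meetings then run about three times per enrolled patient, and a quarterly DSMC review sees about two new patients. So the largest nominal gain falls where existing review is densest. This stands, with the reservation that the plan also allows annual DSMC review.

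Three further points carry weight.

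- The 77% rate belongs to cisplatin-radiation, which these patients might otherwise receive, so whether it demands a pause is a clinical judgement.
- The acceptable rate and error level are choices that the documents do not settle.
- Endpoint 3.2.1 includes expected radiation effects, while one or two treatment-related deaths would not trip the boundary.

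Section 1.6.1 also says this durvalumab dose has shown little toxicity with radiation, and Section 1.5.1 cites 5127 exposed patients. The first statement gives no rate or source. The second covers all indications, as monotherapy or in combination, and is not specific to radiotherapy. Neither supplies a trigger.

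Finally, the undefined criterion in 9.3 is a gap in the final analysis and could be filled without any interim rule. That is true, but using one number for both would be economical.

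**Conclusion.** The gap is real and narrow: surveillance is mandatory, but no number turns it into a pause or an unscheduled DSMC review, and 9.3 relies on an unstated criterion. Adding the number is a cheap improvement.

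Some stronger readings are tempting, and the documents do not support them.

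- A reader might infer that safety is unsupervised. Sections 8.2, 8.4.2, 8.5.3 and 8.6 show otherwise.
- A reader might take 83% as the chance of a useful pause at a true 77%. It includes crossings after all 18 are enrolled; the relevant figure is about 70% or 46%.
- A reader might credit the boundary with sparing 5.4 patients relative to the current plan. That is the upper limit for the stated lag, against a trial that never pauses. The gain over existing oversight is smaller by an amount the documents do not allow one to calculate, and smaller still if most patients were enrolled by Amendment 4.
- A reader might conclude from the uncited reference 29 that a rule was removed. The documents do not say so.

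The size rests on the assumed 50% and 10%, accrual over 6 to 24 months and the 93-day lag. The benefit is meaningful near 77% and small at 50-60%.

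**What to change.** Add to Sections 8.6 and 9.2 a continuous boundary on endpoint 3.2.1 that pauses accrual and sends the data to the existing LCCC DSMC. Tally every Grade 3-5 acute event, serious or not, at each bi-weekly meeting, including patients already treated. State how patients still inside the toxicity window are counted. The investigators should choose and justify the acceptable rate between 34.4% and 77% and print the operating characteristics; the 50%/10% boundary above can serve as a template. A boundary on Grade 4-5 or immune-mediated events is an acceptable alternative if its rate is justified.

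In addition, let any treatment-related death prompt ad hoc DSMC review, because the boundary would not catch it. Fix the 9.3 criterion in advance, either as the same number or separately. What follows a pause stays with the DSMC and the investigators.

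The cost is one paragraph and a small table, using meetings and a committee that already exist. The downside is an unneeded review in some trials: the example is crossed in 10% at a true 50% and 30% at 60%, rates still consistent with the plan's prediction of less toxicity than cisplatin-radiation.

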9.0 STATISTICAL CONSIDERATIONS

9.1 Study Design/Study Endpoints

Primary endpoint is to estimate median 3 year disease free survival (DFS) in patients with intermediate-risk HNSCC treated with adjuvant durvalumab with radiotherapy.

9.2 Sample Size, Accrual and Duration of Accrual

Our evaluable study sample size (N_{total}) is 17, and we will enroll 18 to allow for possible non-evaluable patients. Based on a historical control of 10yr DFS is 19% (Cooper, RTOG 1016), the 3 year DFS is approximated to be 60.8%. Based on this calculation, we will need a sample size of 17 patients, to detect a 23% difference in 3 year DFS with 80% power (table below) and one-sided alpha of 0.1.

Difference from Historical Control	10%	20%	23%	25%
Test significance level, α	0.050	0.050	0.010	0.050
1 or 2 sided test?	1	1	1	1
Null hypothesis proportion, π_0	0.608	0.608	0.608	0.608
Alternative proportion, π_A	0.708	0.808	0.838	0.858
Power (%)	80	80	80	80
n	141	33	17	20

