1.0 BACKGROUND AND RATIONALE

1.1 Study Synopsis

Currently, there is no standard of care for those diagnosed with intermediate risk head and neck squamous cell carcinoma (HNSCC), defined as locally advanced disease with risk features other than extracapsular extension (ECE) or positive margins. Most commonly they are treated with either radiotherapy alone or with concurrent chemo-radiotherapy (cCRT) in the post-surgical setting, with no high level evidence to define which should have chemotherapy added to adjuvant radiotherapy. In patients receiving cCRT, cisplatin is most commonly used. The clinical benefit of cisplatin with radiation therapy in this patient population is questionable and the rate of serious toxicity is high. To address the unmet need for improving systemic treatment options, this multi-center, single arm Phase II trial will evaluate the feasibility of combining radiation therapy with durvalumab as adjuvant therapy for patients with intermediate risk HNSCC.

A total of 18 evaluable subjects will be accrued as depicted in the study schema. The treatment regimen will administer Q3 weekly flat dosing durvalumab (1500 mg) with radiation therapy in cycles 1-3, followed by single agent durvalumab (1500 mg) Q4 weekly for an additional three cycles. Our hypothesis is that durvalumab combined with radiation will have improved 3-year disease free survival (DFS) compared to historical control. Secondarily, we predict there will be fewer Grade 3-5 acute toxicities compared to the combination of radiation therapy and cisplatin. Tissue and blood based correlative studies will characterize the tumor microenvironment both at pre-treatment and in the event of recurrence.

Study Schema

*Radiation therapy is administered per standard radiation oncology regimens, on a daily basis and/or as scheduling during a Monday-Friday work week. Radiation therapy is given concurrently with durvalumab during Cycles 1-3. Durvalumab treatment Cycles 1-3 are 3-week long cycles (total of 9 weeks). Radiation therapy will be delivered at a dose of 2 Gy over 30 fractions totaling a final dose of 60 Gy. Radiation treatment will take 6 weeks (Monday-Friday) or 30 days and occurs for 6 of 9 weeks that define Cycles 1-3. However, due to delays or missed appointments, completion of those

30 fractions may take longer than the allotted 6 weeks and this is allowed. Radiation therapy must be scheduled and completed within Cycels 1-3 and should not extend into Cycle 4.

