1.2 Postoperative Treatment in Head and Neck Cancer: Cisplatin and Radiation as Standard of Care (SOC)

In the modern era, HNSCC has been divided into virally driven cancers due to the human papilloma virus (HPV) and non-HPV cancers, which are typically mediated by smoking and heavy alcohol use. Locally advanced HNSCC is treated with either concurrent cCRT therapy or surgery followed by adjuvant therapy. Commonly, HPV-driven cancers are treated with cCRT and the prognosis is excellent. In contrast, surgery is generally reserved for non-HPV driven cancers or high-risk HPV-positive tumors, both of which are associated with inferior prognosis. Unsurprisingly, postoperative outcomes in HNSCC are poor. In the pre-adjuvant therapy era, local and regional recurrence occurred in 30% of patients and distant recurrence in 25% [1]. Adjuvant radiotherapy (XRT) improves outcomes, however less than 50% patients are disease free at five years.

Two phase 3 studies attempted to improve outcomes for post-operative HNSCC patients by adding cisplatin chemotherapy to adjuvant radiotherapy. RTOG 9501 randomized patients with histologic evidence of invasion of two or more regional lymph nodes, extracapsular extension of nodal disease, or microscopically- involved mucosal margins of resection to either radiotherapy alone or radiotherapy plus three cycles of cisplatin at 100 mg/m² [2, 3]. A second study, EORTC 22931, had a similar randomization, but different inclusion criteria -- pT3 or pT4 and any nodal stage (except T3N0 of the larynx, with negative resection margins), or a tumor stage of 1 or 2 with a nodal stage of 2 or 3 or stage T1/T-N0/1 with unfavorable pathological findings (extranodal spread, positive resection margins, perineural involvement, or vascular tumor embolism) or oral-cavity or oropharyngeal tumors with involved lymph nodes at level IV or V [4].

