A combined analysis of these two trials showed that clear benefit from the addition of cisplatin to radiation therapy was restricted to only patients with extracapsular extension (ECE) or positive surgical margins. This benefit was statistically significant in subgroup analysis in EORTC with a strong trend towards significance in RTOG [5]. Similarly, in long-term follow up (at 9.4 years) of the RTOG study, only patients with ECE or positive margins had a benefit in terms of locoregional failure and disease free survival (DFS). Critically, 10-year disease-free survival (DFS) was poor in cisplatin and radiation treated patients (18%) and only slightly improved compared to patients treated with radiation alone (12%). Perhaps most importantly, no overall survival advantage was noted when comparing cCRT to XRT alone (27% vs 20%, P=0.07) [3]. Thus, the treatment advantage offered by the addition of cisplatin is marginal and there is a low threshold to evaluate experimental therapeutics with the hope of superiority.

Nevertheless, high risk patients, with either ECE or positive surgical margins on their surgical pathology, should receive cisplatin and radiation therapy. In the treatment of patients with intermediate risk factors, defined as having unfavorable pathological factors in the absence of ECE or positive margins, there remains widespread practice variation. These patients may receive either no adjuvant therapy, XRT alone or cCRT, depending on institution, patient, and provider preferences. Importantly, intermediate risk patients who received radiation therapy alone had a locoregional failure risk of 15-35% [6]. To date, there are no published studies comparing radiation therapy versus concurrent systemic therapy plus radiation in this study population. As a result, there is an opportunity to evaluate experimental therapeutics in the intermediate risk population, which may improve outcomes.

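### The one-sided 0.10 error rate in Section 9.2 is not assured, because the 60.8% null is not shown to apply to intermediate-risk patients

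*Combined protocol and SAP*

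**What the plan says.** Section 9.2 bases the null on a "historical control of 10yr DFS is 19"% and continues that "the 3 year DFS is approximated to be 60.8"%. It attributes the figure to RTOG 1016 and gives no treatment arm, population or conversion method. The sample size is 17 evaluable patients (18 enrolled), for a 23-point improvement with 80% power and one-sided alpha 0.1.

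Section 1.1 hypothesises that "durvalumab combined with radiation will have improved 3-year disease free survival (DFS) compared to historical control". It defines the intermediate-risk population as "locally advanced disease with risk features other than extracapsular extension (ECE) or positive margins".

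Section 1.2 describes RTOG 9501 as enrolling patients with invasion of "two or more regional lymph nodes, extracapsular extension of nodal disease, or microscopically- involved mucosal margins of resection". It reports that trial's 10-year DFS as 18% with cisplatin and radiation and 12% with radiation alone. It also calls patients with ECE or positive margins high risk. Its only failure figure specific to this trial's population is that "intermediate risk patients who received radiation therapy alone had a locoregional failure risk of 15-35"%.

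Criterion 4.1.5 admits patients with any one of: perineural invasion, lymphovascular invasion, close margins, a single node above 3 cm, two or more nodes without ECE, or a pT3–4 primary.

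**The concern.** In a single-arm trial the type I error rests on the null being the rate these patients would have had on standard treatment. Here the null seems to come from patients selected partly for the two features that the plan treats as marking high risk, and the trial is aimed at patients who lack them. The one clear overlap is two or more nodes without ECE.

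If intermediate-risk patients on standard adjuvant treatment already do better than 60.8% at three years, favourable case mix could be read as benefit from durvalumab. Sections 9.2 and 9.3 contain nothing to guard against this: no intermediate-risk DFS benchmark, no case-mix adjustment and no sensitivity analysis on the null.

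**Working it through.** **1. The null.** With constant hazard, S(3) = S(10)^(3/10) = 0.19^0.3 = 0.608. This reproduces 60.8%, so the figure is a conversion and not an observed 3-year rate.

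**2. The sample size.** The one-sample normal approximation is n = [(z(1−α)·√(p0·q0) + z(power)·√(p1·q1)) / (p1 − p0)]², with p0 = 0.608, p1 = 0.838, z(0.90) = 1.2816 and z(0.80) = 0.8416. This gives n = [(1.2816 × 0.4882 + 0.8416 × 0.3684) / 0.23]² = 16.55, rounded up to 17, which reproduces the plan. The table prints alpha as 0.010 for this column. That value would give 40, so 0.1 in the text is the operative figure.

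**3. The implied cut.** 0.608 + 1.2816 × √(0.608 × 0.392 / 17) = 0.760.

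**4. The source.** RTOG 1016 appears nowhere else in the document. The two listed references by the author cited in 9.2 (references 2 and 3) are both reports of RTOG 9501, and that trial supplies the only 10-year DFS figures in the background. Those figures are 18% and 12%, not 19%, so the link is an inference.

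**5. Chance that a regimen adding nothing passes.** For a true control rate p, the normal approximation gives 1 − Φ[(0.7597 − p) / √(p(1 − p)/17)]. The exact column is the binomial probability of 14 or more of 17 patients disease free.

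| True control 3-year DFS (assumed) | Normal approximation, cut 76.0% | Exact, 14 or more of 17 |
|---|---|---|
| 52.9% (= 0.12^0.3) | 3% | – |
| 55% | 4% | 1.8% |
| 59.8% (= 0.18^0.3) | 9% | – |
| 60.8% | 10% | 5.3% |
| 65% | 17% | 10.3% |
| 70% | 30% | 20.2% |
| 75% | 46% | 35.3% |

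**6. Which rows are plausible.** Locoregional failure of 15–35% caps DFS at 65–85% before distant failure and death. Assume a further 5–15% have distant failure only (the plan gives no such figure for this group). DFS is then 70–80% at the low end of locoregional failure (1 − 0.15 − 0.05 to 1 − 0.15 − 0.15), 60–70% at 25%, and 50–60% at the high end. Deaths without recurrence would lower all of these. The plan's own range therefore lies on both sides of 60.8%.

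**The case against.** The strongest reply is that the direction of the error is not established, and this stands. Three facts support it.
- If failures come early, constant-hazard conversion overstates 3-year DFS in the source trial, which would offset a case-mix bias.
- Section 1.2 says fewer than half of patients are disease free at five years even with adjuvant radiotherapy. The statement is not specific to intermediate risk, but at constant hazard it puts 3-year DFS below 0.5^0.6 = 66%, where the pass rate is at most about 19%.
- The 15–35% locoregional figure has no stated time point.

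A reader might therefore infer too much in three ways.
- *That the 10% error rate is wrong.* The documents show only that it is unsupported; at 60.8% or below, the normal-approximation test is at or under its nominal level.
- *That the error is near one in two.* This needs a control rate of about 75%, which step 6 reaches only near the low end of locoregional failure.
- *That HPV-positive oropharynx cancers make the null too low.* Section 1.2 does say "Commonly, HPV-driven cancers are treated with cCRT and the prognosis is excellent", but that concerns chemoradiation. It goes on to say that surgery is generally kept for non-HPV or high-risk HPV-positive tumours, both with inferior prognosis, and every patient here has had resection.

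Two further points stand in part. Eligibility is less sharply separated than Section 1.1 suggests: Section 4 has no stand-alone exclusion of ECE or positive margins, and Sections 5.2.1 and 6.2 mention an optional boost to such areas. Those passages need reconciling with Section 1.1, but they leave the case mix less defined and do not validate the null. Also, Sections 2.1 and 3.1 frame the primary aim as estimation, and Section 9.3 states no DFS test, so the cut is implied by the sample-size calculation. As a count, 76.0% means 13 or more of 17, with exact alpha 14.0%; 14 or more gives 5.3%. Section 9.2 nevertheless sizes a test at a stated alpha, and Section 1.1 frames the hypothesis as improvement over control.

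**Conclusion.** The concern holds as a conditional one. Section 9.2 does not show that 60.8% applies to intermediate-risk patients, so the one-sided 0.10 holds only if their 3-year DFS on standard treatment is in fact 60.8%. Across assumed control rates of 52.9% to 70%, the normal-approximation pass rate for a regimen adding nothing runs from about 3% to 30%, and it reaches 46% at 75%.

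This rests on three things: the source being the RTOG 9501 population, which is likely but inferred; control rates that are assumptions; and a pass rule implied by the design. If the source is a different trial, the missing justification remains. Neither the size nor the net direction of the error can be fixed from the documents.

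**What to change.** 1. In 9.2, identify the source trial, arm and population of the 19%, state the constant-hazard conversion, and say that alpha 0.10 applies only if intermediate-risk 3-year DFS on standard treatment is 60.8%.
2. Report the Kaplan-Meier 3-year DFS, already the primary endpoint, with a one-sided 90% lower bound.
3. Show that bound and the false-positive rate against a pre-specified set of reference rates, for example 55%, 60.8%, 65%, 70% and 75%.
4. In 1.1 and 9.2, limit any statement of improvement over historical control to an intermediate-risk reference fixed before analysis. If none can be sourced, describe the result as estimation only.

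The cost is wording and one small table, with no added patients or data. The downside is a weaker claim. For example, 14 of 17 disease free (82%, no censoring) clears 60.8% (exact tail 5.3%) but not 70% (20.2%). Re-powering is not a cheap alternative: keeping 83.8% as the alternative, a 70% null needs about 43 patients by the same formula (45 exact).
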